4.2 Clinical Experience

Probucol clinical trials commenced in the United States in 1977. Dow Chemical Japan, Otsuka Pharmaceutical and Daiichi Pharmaceutical confirmed safety in non-clinical studies and thereafter, also commenced clinical trials in 1984(A1).

Concerns were raised regarding the probucol-induced reduction of serum high-density-lipoprotein (HDL)-cholesterol and potential QT prolongation⁹. Concomitant with the evolution of alternative cholesterol lowering agents, Western countries ceased use of probucol in 1995. However, probucol has remained in use in Japan and other countries including South Korea and China. More recent clinical studies support the concept that probucol should be reconsidered as a drug for coronary heart disease risk-reduction⁹.

This is a FIH trial for Probucol in the treatment of subject with mild to moderate Alzheimer's Disease.

Collectively, results of the *in vitro* and *in vivo* preclinical pharmacology studies support the assessment of LorelcoTM as a disease modifying treatment for subjects with mild to moderate with Alzheimer's disease. It is hypothesised that LorelcoTM will slow the rate of cognitive decline in AD by reducing capillary insult to lipoprotein-amyloid beta; suppressing parenchymal extravasation of lipoprotein-amyloid beta and attenuating neurovascular inflammation.

4.3 Justification for Starting Dose Level and Regimen

The recommended and maximal dose for lowering blood cholesterol is up to 1000mg daily given in two divided doses of 500 mg each with the morning and evening meals. The PIA-study will provide probucol at 250mg b.i.d as recommended in A1 and consistent with recent clinical trials.

The two week initial placebo period will allow for implementation and retraining to assist with dose compliance, without giving participants the intervention drug.

The dose level and regime begins at 250 mg a day (Week 3) to monitor for gastrointestinal safety events (as described in section $\underline{6.1}$).

4.4 Risk Assessment and Guidance for Investigators

Prolongation of the QT interval can occur in patients on probucol. Clinical trials by Yamashita¹⁰ and Kang¹¹ reported significantly more prolonged QT interval adverse events in individuals taking probucol (LorelcoTM), compared to controls. While drug-induced prolonged QT interval can be associated with significant adverse side effects such as ventricular arrhythmia (torsades de pointes), studies involving the use of 500 mg of Probucol daily, reported probucol-induced prolonged QT interval was not associated with, or increased the incidence of, ventricular arrhythmias. Furthermore, Walldius¹² reported that there was no significant difference in cardiovascular clinical events between individuals taking probucol and controls. No malignant arrhythmias or torsades de pointes were reported for either group. The absence of arrhythmias may be due to strict prolonged QT/QTc interval exclusion

Protocol Version 4, 06 OCT 2021

Confidential

Page 19 of 70

criteria. While there is no consensus on upper limit corrected QT/QTc interval values, many studies adopt an absolute QT/QTc interval prolongation of > 500ms. This reduces the risk of ventricular arrhythmia, as participants are discontinued prior to prolonged QT intervals associated with arrhythmia.

While QT prolongation by probucol may not enhance the occurrence of lethal ventricular arrhythmias, studies have identified several clinical risk factors for drug-induced arrhythmias, including probucol. These include;

- Cardiac factors (including congenital long QT syndrome, family history of sudden cardiac death, bradycardia)
- Myocardial hypertrophy
- Heart failure
- Liver disease
- Thyroid Dysfunction
- Renal or hepatic impairment

The above clinical risk factors should be considered prior to treatment with probucol¹³.

Further information regarding Lorelco $^{\text{TM}}$ is available in the Investigator's Brochure.

Protocol Version 4, 06 OCT 2021

Confidential

Page 20 of 70

5 STUDY OBJECTIVES AND ENDPOINTS

The study objectives and endpoints are provided in Table 2, below.

Table 1. Study Objectives and Endpoints for Study PIA-2020

Objective(s)	Endpoint(s)
Primary	
• To evaluate the preliminary efficacy of 250 mg BID Lorelco TM on cognitive performance in Alzheimer's patients over a 102 week treatment period	Cognitive performance parameters include (but are not limited to): • Cognitive Subscale test (ADAS-Cog)
Secondary	
To evaluate:	 PET Scan visual assessment of amyloid load quantitative assessment of amyloid burden MRI Scan volumetric changes in the brain cerebral amyloid abundance Quality of life parameters to be assessed include (but are not limited to): Alzheimer's Disease Co-operative Study Mild Cognitive Impairment Activities of Daily Living scale (ADCS-MCI-ADL24) Depression Anxiety Stress Scale (DASS-21)
To assess the safety and tolerability of Lorelco™ in patients with Alzheimer's Disease	Safety and tolerability endpoints include: Incidence, type and severity of AEs Dose-limiting toxicities (DLTs) Changes from baseline in: electrocardiogram (ECG) parameters vital sign measurements body weight physical examination finding clinical laboratory parameters

Curtin University Study Protocol
Protocol No.: PIA-2020

6 STUDY DESIGN

6.1 Design Type and Description

This is a Phase 2, randomised, double blind, placebo-controlled parallel group study in adults with mild to moderate AD.

The study will assess the efficacy, safety and tolerability of the treatment of Alzheimer's disease in approximately 300 subjects with LorelcoTM.

After consenting to participate in the study, screening procedures will occur between Days - 24 and -1. All subjects must have measurable mild or moderate Alzheimer's disease, and accordingly screening procedures will include:

- o A positive amyloid biomarker (PET scan) indicative of AD pathology,
- o Mini-mental-state examination (MMSE) score of 22 or greater,
- Free and cued selective reminding test (FCSRT) cueing index of 0.79 or less OR free recall score ≤17
- o Clinical Dementia Rating (CDR) global score of 0.5 or 1.0.
- o A study partner (partner/spouse/carer) consents to the minimum requirements:
 - Study partner will attend at least one screening visit
 - Study partner will be available via phone or in person to provide information to the study as required

Eligible subjects will be randomized in a 1:1 (active:placebo) ratio and return to the study unit on Day 1.

The dosing schedule for subjects is shown in Table 2. The two week initial placebo period will allow for implementation and retraining to assist with dose compliance, without giving participants the intervention drug. The dose level and regime begins at 250 mg a day (Week 3) to monitor for gastrointestinal safety events.

Table 2. Planned Subject Dosing Schedule

Week	Dose Level	Total Daily Lorelco TM Dose (mg)
Week 1 and 2	1 x placebo taken in the morning, with food.	0 mg
Week 3	1 x 250 mg Lorelco [™] (or matching placebo) taken in the morning, with food.	250 mg (or placebo 0 mg)
Week 4 -104	 1 x 250 mg probucol (or matching placebo) taken in the morning, with food. 1 x 250 mg probucol (or matching placebo) taken in the evening, with food. 	500 mg (or placebo 0 mg)

Subjects will self-administer LorelcoTM or placebo in the clinic under the supervision of site staff on Days 1 (±2 days) on Weeks 1, 2, 3, 4, 5, 15, 26, 39, 52, 65, 78 and 104. All other doses will be self-administered at home, or under the supervision of the designated study partner as appropriate. LorelcoTM and Placebo will be provided in a Webster pack or equivalent to assist with dose compliance.

[figure not shown]
Patients will also undertake safety and other assessments as required on Days 1 (± 2 days) on Weeks 1, 2, 3, 4, 5, 15, 26, 39, 52, 65, 78 and 104.

A study design overview is shown in Figure 1.
Protocol Version 4, 06 OCT 2021 Confidential

Page 22 of 70

Curtin University Study Protocol
Protocol No.: PIA-2020

Figure 1. Study Design Overview

Patients will be screened between Day -56 to Day -1.

Safety and tolerability assessments will include vital signs, 12-lead ECGs, physical examinations, clinical laboratory tests (haematology, serum chemistry, coagulation, lipid analysis and urinalysis), and AE monitoring, as described in Section 11.8. Blood samples will be collected at specified times, as described in the schedule of assessments (APPENDIX 1).

Efficacy assessments include imaging using, PET scan and Magnetic Resonance Imaging (MRI) as described in Section 11.9. Imaging assessments will be performed at screening, and the 104 week visit or at last study visit if subject discontinues.

A final end of study visit will occur 4 weeks (\pm 2 weeks) following the last study drug administration.

There are no scheduled overnight confinement periods, however if patients experience any clinically significant adverse events (AEs) during the study, they may be admitted to the clinical facility for further observation at the discretion of the PI.

In the event of strong clinical benefit, and at the discretion of the study doctor, a participant may be reinstated in the study 4 weeks after discontinuation of the participant due to AE. This will be evaluated on a case by case basis.

Regardless of perceived benefit, participants cannot continue probucol at the end of the study as LorelcoTM is not approved for use in Australia. If strong clinical support is identified in the study, this will support effectiveness and phase III trials.

LorelcoTM will be evaluated at a single dose levels with dose increasing to BID by week 4 (Table 2). Thirty patients will initially be enrolled into single-patient cohorts and will be observed during the evaluation period (Week 2 Day 1 to Week 6).

If the patients do not experience any ≥Grade 2 AEs that are deemed related to study treatment, then additional patients may be dosed. The decision to commence dosing in additional patients will be at the discretion of the SRC following review of all AEs, clinical findings, laboratory results.

If in any of the single-patient cohorts a patient experiences a \geq Grade 2 AE that is not clearly attributed to underlying disease, other medical conditions, or concomitant medications or procedures during the initial safety period, an additional 30 patients will be enrolled at that dose level and evaluated.

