1 PROTOCOL SYNOPSIS

Study Title	A Double-Blind, Placebo Controlled, Randomised Phase II Trial of Probucol in Alzheimer's Disease (PIA-Study): The Impact on Cognition
Study Number	PIA-2020
Phase	Phase II
Number of Clinical Sites	Up to 2 sites within Australia
Study Population	Subjects with mild to moderate Alzheimer's Disease
v i	Patient-specific selection criteria apply, as described in the study eligibility criteria.
Patient Number	Up to 314 patients are planned to be recruited
Study Treatment	Lorelco [™] Tablets: 250 mg will be administered in this study. Lorelco [™] will be over-encapsulated inside an opaque capsule shell and backfilled with Microcrystalline cellulose.
	Intermediate doses may also be evaluated at the discretion of the Sponsor and in consultation with the Safety Review Committee (SRC).
	Placebo : Matched capsules
Route of Administration	Oral
Number of doses per treatment	Week 1 and 2: One placebo capsule taken in the morning, with food.
	Week 3: One 250 mg Lorelco [™] (or matching placebo) taken in the morning, with food.
	Week 4 to 104: One 250 mg Lorelco TM (or matching placebo) taken in the morning, with food. One 250 mg Lorelco TM (or matching placebo) taken in the evening, with food.
Study Duration	The study timeframe will include up to a 56-day screening period, 2 week placebo week treatment period and a 104 week active or placebo treatment period, and a follow-up visit 4 weeks from the last dose of study treatment.
	Patients will continue on the study unless they have unacceptable adverse events, unacceptable QT/QTc interval prolongation, they withdraw informed consent, or are withdrawn from the study.
	In the event of strong clinical benefit, and at the discretion of the study doctor, a participant may be reinstated in the study 4 weeks after discontinuation of the participant due to AE. This will be evaluated on a case by case basis.
	Regardless of perceived benefit, participants cannot continue probucol at the

Protocol Version 4, 06 OCT 2021

Confidential

Page 4 of 70

	Study Protocol
Curtin University	Protocol No.: PIA-2020

PRINCIPAL INVESTIGATOR SIGNATURE PAGE

Study Title:		
A Double-Blind, Placebo Controlled, Randomised Phase II Trial of Probucol in Alzheimer's Disease (PIA-Study): The Impact on Cognition		
[name]	20 October 2021	
Signature of Principal Investigator	Date	
[name]		
Printed Name of Principal Investigator		
Institution Name: Australian Alzheimer's Research F	oundation	

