	 A positive amyloid biomarker (PET scan) indicative of AD pathology, Mini-mental-state examination (MMSE) score of 22 or greater, Free and cued selective reminding test (FCSRT) cueing index of 0.79 or less OR free recall score ≤17 Clinical Dementia Rating (CDR) global score of 0.5 or 1.0. A study partner (partner/spouse/carer) consents to the minimum requirements: Study partner will attend at least one screening visit Study partner will be available via phone or in person to
	 Study partner will be available via phone or in person to provide information to the study as required Eligible subjects will be randomized in a 1:1 (active:placebo) ratio and return to the study unit on Day 1. Subjects will be dosed as: Week 1 and 2: 1 x placebo taken in the morning, with food Week 3: 1 x 250 mg LorelcoTM (or matching placebo) taken in the morning, with food. Week 4 - 104: 1 x 250 mg LorelcoTM (or matching placebo) taken in the morning, with food. 1 x 250 mg probucol (or matching placebo) taken in the evening, with food.
Duration of Study and Dose Administration Stopping Rules	Patients may continue to receive study medication until week 104 unless evidence of unacceptable toxicities, they withdraw consent or are withdrawn. The primary study analysis will occur when target enrolment is complete, and each patient either completes 104 weeks on study, or withdraws. If treatment during the study is interrupted, Lorelco TM may be reinitiated. At the discretion of the principal investigator, a participant may be reinstated in the study 4 weeks after discontinuation of the participant. This will be evaluated by the Investigator and the DSMB on a case by case basis. All participants will take part in a safety evaluation 4 weeks following discontinuation.

Protocol Version 4, 06 OCT 2021

Confidential

Page 9 of 70

Study Protocol

Curtin University	Protocol No.: PIA-2020
Study Assessments	
Safety and Tolerability	 Medical history Evaluation of any on-study AEs and concomitant medication use Height and weight Physical examination Vital signs (supine systolic and diastolic blood pressure, heart rate, respiratory rate, body temperature) 12-lead ECGs Analysis of laboratory safety markers (including haematology, serum chemistry, coagulation, lipid analysis and urinalysis)

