6.2 Duration of Therapy and Patient Withdrawal Criteria

In the absence of toxicity or unacceptable adverse events, it is expected that patients will remain on study treatment for 104 weeks. Patients will receive study drug unless they have unacceptable toxicity, withdraw informed consent, or are withdrawn from the study.

Reasons for withdrawal of study therapy regardless of length of time on study include the following:

- Unacceptable toxicity, defined as:
 - Occurrence of an AE that is related to treatment with the study drug which, compromises the patient's ability to continue; or
 - o Persistent AE requiring a delay of therapy for more than 4 weeks (28 days).
- Intercurrent illness that requires a delay of therapy for more than 4 weeks (28 days).

Protocol Version 4, 06 OCT 2021

Confidential

Page 24 of 70

- Patient chooses to withdraw from the study.
- Patient becomes pregnant.
- Patient noncompliance.
- Any other reason, in the opinion of the Investigator, that renders the patient no longer appropriate for study continuation.

Patients will be advised that they are free to withdraw from the study at any time for any reason or, if necessary, the Investigator, or medically qualified delegate, may discontinue a patient from the study to protect the patient's health.

The date and reasons for withdrawal/discontinuation will be recorded in the electronic case report form (eCRF) and included in the final clinical study report, along with any AEs and necessary medical treatment.

In the event that a patient is discontinued from the study due to an SAE, the Investigator, or medically qualified delegate, will evaluate the urgency of the event. If the situation warrants, the Investigator, or medically qualified delegate, will take appropriate diagnostic and therapeutic measures and make attempts to notify the Sponsor MM. If the situation is not an immediate emergency, the Investigator, or medically qualified delegate, at the clinical study facility will attempt to contact the Sponsor MM for consultation. No medical help, diagnosis, or advice will be withheld from the patient due to an inability to contact the Investigator or medically qualified delegate. The patient will be encouraged to remain available for follow-up medical monitoring. The Sponsor will be notified as soon as possible of any patient withdrawals.

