6.7 Dose Stopping Rules and Individual Dosage Adjustments

Dosing may be stopped or modified if suspected adverse drug reactions, changes in vital signs, ECGs, or clinical laboratory results are observed, and these changes pose a significant health risk. Of particular note for dose discontinuation are the following criteria;

- Corrected QT/QTc interval is in excess of 500 ms, or if it increases > 50 ms compared to baseline (baseline will be calculated as the mean of two time points, screening and baseline day 1).
- Occurrence of QT/QTc interval prolongation in association with symptoms of arrhythmia
- Subsequent prescription of a drug with potential QTc prolongation (Antimalarial; Macrolides; Quinolones; Triazole antifungals; Anti-arrhythmic; Antiemetic; Antidepressant; Antipsychotics)
- Evidence of Liver dysfunction, or primary biliary cirrhosis
- If for any reason the Investigator determines that continued participation in the trial is not in the participant's best interest.

The study may be terminated at any point in time at the discretion of the Sponsor.

Clinically or medically significant suspected adverse drug reactions, and SAEs considered to be related to study procedures will be followed until resolved or considered stable.

If an unscheduled interruption of treatment occurs, the PI should notify the Sponsor (via the Clinical Research Organization [CRO]) at the earliest possible time. A missed dose will not be made up. In the event that a patient requires an unscheduled interruption of treatment under conditions other than those associated with toxicity, the case will be reviewed by the PI and the MM, and discussed with the Sponsor/CRO to determine whether such a patient will be allowed to resume treatment.

At the discretion of the Investigator, a participant may be reinstated in the study 4 weeks after discontinuation of the participant. This will be evaluated on a case by case basis, and will also be reviewed by the DSMB. Participants will have a safety evaluation 4 weeks following study drug discontinuation.

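### Four passages give incompatible rules for reinstating a participant after discontinuation, and leave the 28-day limit and QTc stops unaddressed

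*Protocol*

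**What the plan says.** Four passages of the protocol deal with reinstatement.

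- **Synopsis, Study Duration:** "In the event of strong clinical benefit, and at the discretion of the study doctor, a participant may be reinstated in the study 4 weeks"; the rule is for stops caused by an AE. Evaluation is case by case and no DSMB role is stated.
- **Section 6.1:** the same rule, under the same benefit condition and the same discretion: "a participant may be reinstated in the study 4 weeks after discontinuation of the participant due to AE".
- **Synopsis, Duration of Study and Dose Administration Stopping Rules:** "At the discretion of the principal investigator, a participant may be reinstated in the study 4 weeks after discontinuation of the participant". On the DSMB, this entry adds: "This will be evaluated by the Investigator and the DSMB on a case by case basis".
- **Section 6.7:** the Investigator has the discretion, again 4 weeks after discontinuation and for any cause. It adds: "This will be evaluated on a case by case basis, and will also be reviewed by the DSMB".

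Section 6.2 lists grounds for taking a patient off study treatment. One is "Persistent AE requiring a delay of therapy for more than 4 weeks (28 days"). Another is a drug-related AE that undermines the patient's ability to carry on. It does not mention reinstatement.

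Section 6.8 puts participants who stop before Week 104 on a modified schedule. The only visit it names is 4 weeks after the last study drug.

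**The concern.** Section 4.4 cites trials in which prolonged-QT adverse events were significantly more frequent on probucol, so re-dosing after a safety stop is a situation the trial should expect. If the texts disagree on when re-dosing is allowed and who must see the case first, two sites can treat the same patient differently and both be following the protocol.

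There is also a statistical side. Two of the four passages make return depend on perceived benefit, in a trial whose primary outcome is cognition. If reinstated participants go on supplying ADAS-Cog scores and the others do not, the late data over-represent those who were doing well.

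**Working it through.** The protocol gives no figure on this point, so the main check sets the passages side by side.

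| | Synopsis (Study Duration) and 6.1 | Synopsis stopping rules | 6.7 |
|---|---|---|---|
| Trigger | AE stop | Any discontinuation | Any discontinuation |
| Benefit condition | Strong clinical benefit (not defined) | None | None |
| Discretion | Study doctor | Principal investigator | Investigator |
| DSMB | Not stated | Evaluates with the Investigator | Reviews |

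Two cases show that the columns cannot all be followed.

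1. AE stopper without strong benefit: 6.7 permits reinstatement; 6.1 gives no basis for it.
2. AE stopper with strong benefit: 6.1 lets the study doctor proceed with no DSMB step stated; 6.7 calls for DSMB review.

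Treating study doctor, Investigator and principal investigator as one person removes only the third row. Section 6.7 has a further route for interruptions not due to toxicity, where "the case will be reviewed by the PI and the MM, and discussed with the Sponsor/CRO". That is a different situation and is not counted as a conflict.

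**28-day limit.** Reinstatement at 4 weeks is 4 × 7 = day 28. The 6.2 ground needs a delay of more than 28 days. Day 28 is within the limit and day 29 exceeds it, so the rules meet at day 28. No latest restart date is given, and 6.2 does not say whether withdrawal for toxicity can be reversed.

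**QTc and arrhythmia stops.** Section 6.7 lists these among its discontinuation criteria. No reinstatement passage says whether they are included or excluded.

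**Selection of late scores.** A simulation tested when the mechanism matters.

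- From the protocol: ADAS-Cog at baseline and Weeks 26, 52, 78 and 104 (11.6.2); target effect 0.25 × 1.10 = 0.275 standardised units; SD of change 0.83 (7.1, 13.1).
- Assumed, not in the protocol: intercept SD 1; residual SD 0.3, so slope SD = √(0.83² − 2 × 0.3²) = 0.71; AE stops after the Week 26, 52 or 78 visit, in 5% on placebo and 5%, 15% or 25% on active; return if the two-year rate of decline is below 0.55, half the placebo rate; no scores after a stop without return.
- Method: generalised least squares with known covariance in place of the random intercept and slope model, 400,000 simulated patients per scenario. True difference −0.275.

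| AE stops, active / placebo | Return decided on | Mixed model | Week 104 observed cases |
|---|---|---|---|
| 5% / 5% | recorded scores | −0.274 | −0.276 |
| 5% / 5% | unrecorded judgement | −0.277 | −0.277 |
| 15% / 5% | recorded scores | −0.276 | −0.303 |
| 15% / 5% | unrecorded judgement | −0.295 | −0.313 |
| 25% / 5% | recorded scores | −0.274 | −0.332 |
| 25% / 5% | unrecorded judgement | −0.306 | −0.345 |

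With no reinstatement at all, every estimate lies between −0.274 and −0.276. Equal stopping gives no material bias. Unequal stopping distorts the observed-case contrast under either basis for return. The mixed model moves only when stopping is unequal and the decision uses information outside the recorded scores: by 0.295 − 0.275 = 0.020 (7% of 0.275) or 0.306 − 0.275 = 0.031 (11%).

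**The case against.** The strongest reply is that much of this is silence, not conflict. Section 6.1 does not exclude the DSMB. Section 6.7 holds the QTc criteria and the DSMB review together. Section 12.8 makes blinded ECG data available to the DSMB after a severe effect such as QT prolongation, with 3-monthly ECG review at first. A reader might infer that a study doctor may re-expose a QTc stopper with nobody else looking; the documents do not support that. What survives is that the trigger and the benefit condition still differ, and that ECG review in 12.8 is not a stated step before re-dosing.

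A reader might also infer that 6.2 flatly forbids what 6.1 allows. It does not: an AE that has resolved no longer requires a delay, 6.2 does not call withdrawal irreversible, and the two limits meet at day 28. Nor can the ±2-week window in 6.1 be used to push reinstatement past that limit. It belongs to the final end-of-study visit; the post-discontinuation safety evaluation in 6.7 has no window, and no passage ties reinstatement to either visit.

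On bias, the stated primary analysis is an intention-to-treat mixed model, the decision is blinded, and the rule applies to both arms. Section 4.4 gives an imbalance in QT events, not in stopping rates. The contents of the modified schedule in 6.8 are not listed, so loss of ADAS-Cog after a stop is an inference. These points stand. They reduce the bias issue to a conditional one, but section 13.6 also plans change-score correlations and GEE and general linear model comparisons, and section 13 rules out imputation.

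**Conclusion.** The conflict holds on the text. The four passages disagree on the triggering event, the benefit condition and the DSMB's role, and reading them together does not remove the disagreement. Their relation to the 28-day limit and to QTc or arrhythmia stops is unstated. Because this governs re-dosing after a safety stop, it should be settled by amendment.

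The selection effect is a sound but secondary concern. Observed-case and change-score summaries are exposed if AE stops differ by arm. The primary mixed model is affected only if, in addition, the judgement draws on more than recorded scores. The percentages in the check rest on assumed stopping rates, an assumed restart threshold and no follow-up after an unreinstated stop. They show the conditions under which bias arises and are not an estimate for this trial.

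**What to change.** Reconcile the passages into one reinstatement rule, stated once (section 6.7 is the natural place) and cross-referenced from both synopsis entries, 6.1 and 6.2. It should state:

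- the triggering event;
- any benefit condition and, if one is kept, its definition;
- who decides;
- the DSMB's role, and whether it comes before re-dosing;
- the relation to the 28-day limit in 6.2;
- whether participants stopped under the 6.7 QTc or arrhythmia criteria are included.

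Which clinical rule applies is for the sponsor and the DSMB.

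Separately, state in 6.8 that the scheduled ADAS-Cog visits continue for consenting participants whether or not they are reinstated. Barring ADAS-Cog results from the reinstatement decision is not advised: it would in effect choose a clinical rule, and it could shift the decision from recorded scores, where the mixed model held, to unrecorded impressions, where it did not.

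The cost is amendment wording and some off-drug assessment visits.
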